Briefly describe study design and anticipated enrollment, i.e., number of subjects to be enrolled by researchers study-wide and by Partners researchers. Provide a brief summary of the eligibility criteria (for example, age range, gender, medical condition). Include any local site restrictions, for example, “Enrollment at Partners will be limited to adults although the sponsor’s protocol is open to both children and adults.”

A total of 200 ED patients will be recruited and randomized for this project.

Inclusion criteria: 1) age \geq 18 years patients and either a parent/guardian of a pediatric/cognitively disabled patient in the MGH ED, 2) triaged to the Acute, CDU, Fast Track, Urgent, and Pediatrics areas, 3) English- or Spanish-speaking, and 4) capable of informed consent. *Exclusion criteria:* 1) patients unwilling to have the interview audio-recorded, 2) medically unstable patients, and 3) Section 12, lack of capacity medical hold (yellow paper), sexual assault, child abuse, and emotionally distressed patients.

Bilingual research assistants (RA) will screen patients for eligibility based on the above predetermined criteria. Potential study participants will be approached by trained RAs who will verbally consent patients for participation in the study. Patients who provide consent will be randomized to oral v. written (iPad) screening for completion of the Partners HealthCare HRSN screening tool. We plan to enroll 100 patients into each of the oral v. iPad screening groups, to examine potential differences in satisfaction and screening responses. A subset of enrolled patients will be invited to participate in an in-depth interview. Participants will be compensated \$20 for the additional time to complete the interview component of the study. We will purposively sample enrolled participants to balance recruitment across 4 groups defined by screening strategy (oral v. iPad) and health literacy (high v. limited). The sampling strategy is purposive, designed to make sure the full range of themes is elicited within each prespecified group. We will enroll in the interview portion of the study until thematic saturation is reached in each of the four groups.

Briefly describe study procedures. Include any local site restrictions, for example, “Subjects enrolled at Partners will not participate in the pharmacokinetic portion of the study.” Describe study endpoints.

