Bilingual research assistants (RA) will screen patients for eligibility based on the predetermined criteria and approach eligible patients with a brief description of the study and opportunity for participation. Interested participants will complete a verbal consent process to reduce the barriers to participation, a brief demographic questionnaire, and an assessment of health literacy (Newest Vital Sign) followed by the Partners Healthcare HRSN screener randomized to an oral v. iPad screening strategy. Randomization will occur after consent. Randomization will be operationalized through use of a randomization list. We will make 500 randomization assignments for an expected study enrollment of 200.

After completion of the screening tool, participants will complete a secondary questionnaire asking about satisfaction with the process, the presence of additional HRSN not recorded by the Partners HealthCare screener, and their perspectives on screening. At the conclusion, all participants will be provided with standardized, bilingual list of community resources to address each of the screening domains. For patients who explicitly request assistance with making these connections, the clinical team will be informed, and a Social Services consult (or ED navigator consult when appropriate) will be recommended.

A subset of enrolled patients will be invited to participate in an in-depth interview. We have chosen to use qualitative interviews to identify the range of opinions regarding screening for HRSN in the ED setting. We will purposively sample to balance recruitment across 4 groups defined by screening strategy (oral v. iPad) and health literacy (high v. limited). The sampling strategy is purposive, designed to make sure the full range of themes is elicited within each prespecified group. Interviews are continued until thematic saturation is reached for each group, the point at which interviews are no longer revealing new information about the primary topic of interest. Although there is no formal sample size for qualitative studies, thematic saturation is generally reached by 12 interviews per group,² and therefore we anticipate completing 48 interviews. As we anticipate fewer Spanish-speaking participants based on ED demographics, all Spanish-speaking patients will be invited to participate in the qualitative interview to ensure a diverse representation of perspectives. These 30-minute qualitative interviews will cover

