domains regarding screening preferences, barriers and facilitators to disclosure of HRSN in the ED, perception of screening practices, and the opportunity to identify HRSN that may have been missed by the Partners HealthCare HRSN screening tool. All interviews will be recorded, encryption-stored, professionally transcribed, and qualitative software will be used for analysis.

¹ Osborn CY, Weiss BD, Davis TC, et al. Measuring adult literacy in health care: performance of the newest vital sign. *Am J Health Behav.* 2007;31(Suppl 1):S36-46.

² Guest G, Bunce A, Johnson L. How many interviews are enough? An experiment with data saturation and variability. *Field Methods.* 2006;18(1):59-82.

For studies involving treatment or diagnosis, provide information about standard of care at Partners (e.g., BWH, MGH) and indicate how the study procedures differ from standard care. Provide information on available alternative treatments, procedures, or methods of diagnosis.

N/A

Describe how risks to subjects are minimized, for example, by using procedures which are consistent with sound research design and which do not unnecessarily expose subjects to risk or by using procedures already being performed on the subject for diagnostic or treatment purposes.

Although it is not anticipated that any of the screening or qualitative interview questions will cause emotional discomfort or distress, participants are informed that they may decline to answer any questions and/or withdraw from the study altogether.

Describe explicitly the methods for ensuring the safety of subjects. Provide objective criteria for removing a subject from the study, for example, objective criteria for worsening disease/lack of improvement and/or unacceptable adverse events. The inclusion of objective drop criteria is especially important in studies designed with placebo control groups.

Should a patient or parent wish to withdraw at any point they can do so. In addition, if the clinical team feels a patient is no longer appropriate to participate in the study (e.g., worsening disease of the patient or child, need for potentially distressing clinical communication), we will stop the interview and use only the portion of the data already collected.

FORESEEABLE RISKS AND DISCOMFORTS

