Provide details of remuneration, when applicable. Even when subjects may derive medical benefit from participation, it is often the case that extra hospital visits, meals at the hospital, parking fees or other inconveniences will result in additional out-of-pocket expenses related to study participation. Investigators may wish to consider providing reimbursement for such expenses when funding is available

For guidance, refer to the following Partners policies:

Recruitment of Research Subjects

https://partnershealthcare-public.sharepoint.com/ClinicalResearch/Recruitment_Of_Research_Subjects.pdf

Guidelines for Advertisements for Recruiting Subjects

https://partnershealthcare-public.sharepoint.com/ClinicalResearch/Guidelines_For_Advertisements.1.11.pdf

Remuneration for Research Subjects

https://partnershealthcare-public.sharepoint.com/ClinicalResearch/Remuneration_for_Research_Subjects.pdf

CONSENT PROCEDURES

Explain in detail how, when, where, and by whom consent is obtained, and the timing of consent (i.e., how long subjects will be given to consider participation). For most studies involving more than minimal risk and all studies involving investigational drugs/devices, a licensed physician investigator must obtain informed consent. When subjects are to be enrolled from among the investigators' own patients, describe how the potential for coercion will be avoided.

Informed consent for participation will be obtained from all adult patients and parent/guardians of underage (age < 18 years) patients. There will be no HRSN screener or qualitative interview participation by a child. We are asking only the parent/guardian who will participate in the verbal consent process, to participate in the study.

We are particularly interested in perspectives of participants with limited health literacy and concerned that written informed consent could be a disproportionate barrier to enrollment for patients with limited health literacy. Therefore, we request permission to obtain verbal informed consent to reduce literacy related barriers to participation. RAs will consent eligible patients and parents/guardians of eligible pediatric patients using a verbal consent process while individuals are in a private room. Parents will be given an information sheet in either English or Spanish.

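### Does scheduling the satisfaction questionnaire after the screener leave early stoppers without a value and bias the oral v. iPad comparison?

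*Protocol*

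**What the plan says.** All of the relevant text is in the Protocol.

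- **Size and purpose** (Research Design and Methods, study design): "A total of 200 ED patients will be recruited and randomized for this project". The split and its aim are given as "We plan to enroll 100 patients into each of the oral v. iPad screening groups, to examine potential differences in satisfaction and screening responses". Satisfaction is therefore one of two outcomes to be compared between arms.
- **Order of events** (Research Design and Methods, study procedures): "Randomization will occur after consent". Demographic questions, a health literacy test and the screener in the assigned mode are all listed after consent. Then: "After completion of the screening tool, participants will complete a secondary questionnaire asking about satisfaction with the process". The same questionnaire asks about needs that the screener missed and about views on screening.
- **Stopping** (Research Design and Methods, risk minimisation and safety): "participants are informed that they may decline to answer any questions and/or withdraw from the study altogether", and "Should a patient or parent wish to withdraw at any point they can do so". If the clinical team judges that a patient should not continue, the session ends and the data gathered so far are kept.
- **Records**: assignments come from a randomisation list (study procedures). The research assistant signs an enrolment record for each verbal consent (Consent Procedures). Data files are identified by study number (Privacy and Confidentiality). No section describes a field for completion status or reason for stopping.

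**The concern.** Finishing the screener happens after randomisation, and the mode may affect it in either direction. Background and Significance describes ED patients as possibly ill, exhausted and often interrupted, so some may stop partway. Consent Procedures adds "We are particularly interested in perspectives of participants with limited health literacy", and such patients might find a tablet harder.

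Read strictly, the schedule gives a satisfaction value only to those who finish. A comparison among finishers would then lose the protection of randomisation: the mode that drives away more dissatisfied people would show the higher satisfaction among those who remain. Stopping is also evidence on acceptability, which the hypothesis names. An analysis plan can choose how to treat missing values, but it cannot recover answers or reasons that nobody collected. That makes the order of data collection a fair thing to question in a protocol, even with the analysis plan not at hand.

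**Working it through.** **The plan's own figure.** 100 + 100 = 200 agrees with the stated total. The protocol gives no satisfaction rate, stopping rate, effect size, significance level or power, so nothing further can be reproduced. Every rate below is an assumption.

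**Size of the bias if non-completers are never asked.** Let t be true satisfaction in all randomised (equal in both arms), q the share not completing, and s the satisfaction of non-completers. Satisfaction among completers is

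(t − q·s) / (1 − q).

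With t = 0.70:

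| q | s = 0.3 | s = 0.5 |
|---|---|---|
| 0.20 | (0.70 − 0.06)/0.80 = 0.800 | (0.70 − 0.10)/0.80 = 0.750 |
| 0.15 | (0.70 − 0.045)/0.85 = 0.771 | (0.70 − 0.075)/0.85 = 0.735 |
| 0.10 | (0.70 − 0.03)/0.90 = 0.744 | (0.70 − 0.05)/0.90 = 0.722 |
| 0.05 | (0.70 − 0.015)/0.95 = 0.721 | (0.70 − 0.025)/0.95 = 0.711 |
| 0.02 | (0.70 − 0.006)/0.98 = 0.708 | (0.70 − 0.01)/0.98 = 0.704 |

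The false difference between arms is the difference between two rows. The rejection rate is that of a pooled two-sided 5% z test on completers, by exact binomial enumeration; without bias it would be about 5%.

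| Non-completion | False difference (points; s = 0.5 to s = 0.3) | Rejection rate |
|---|---|---|
| 20% v. 5% | 3.9 to 7.9 | 9% to 23% |
| 15% v. 5% | 2.5 to 5.0 | 7% to 12% |
| 10% v. 5% | 1.2 to 2.3 | 5.4% to 6.5% |
| 5% v. 2% | 0.6 to 1.3 | 5.2% to 5.6% |
| 10% v. 10% | 0 | 5% |

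Swapping the arms reverses the sign.

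**Scale.** With 100 per arm, a two-sided 5% test and 80% power (pooled-variance formula), the detectable change from 70% is to 86.3% (16.3 points up) or to 50.7% (19.3 points down). Every false difference in the table is smaller.

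**Extreme case.** If every non-completer is dissatisfied (s = 0), 15% v. 5% gives 0.700/0.85 − 0.700/0.95 = 0.824 − 0.737 = 8.7 points (rejection 29%). With t = 0.80 it gives 0.941 − 0.842 = 9.9 points (58%). At 20% v. 5% the gaps are 0.875 − 0.737 = 13.8 points for t = 0.70 and 1.000 − 0.842 = 15.8 points for t = 0.80. The last exceeds the 13.4 points detectable upward from 80%. The bias is thus not bounded at a small value; its size depends on unknown rates.

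**Whom a different sentence would reach.** Take the ways a participant can fail to finish:

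1. Declines the remaining items but stays. The safety text allows this, and the satisfaction questionnaire follows as scheduled.
2. Withdraws from the study. No value is obtained under any wording.
3. Is stopped by the clinical team. The stop rule keeps only what has been gathered, and a reworded schedule would not alter it.
4. Quits the screener without declining item by item, yet would answer further questions. The text is silent on this group.

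The calculation above treats groups 2 to 4 together as the loss. Only group 4 could be recovered by clearer wording, so the table overstates what a change would gain.

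**What can be seen afterwards.** The randomisation list, the enrolment records and files held by study number should allow a randomised participant without a satisfaction questionnaire to be counted by arm.

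**The case for a change.** The strongest argument for a change is that it would be cheap and could not be made later: one sentence offering the satisfaction items whether or not the screener was finished, and one field for status and reason. A declined item and an abandoned screener may look alike on paper, and the reason for stopping would be lost unless someone writes it down. Under the extreme assumptions the bias could produce a false positive more often than not.

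Part of this stands. The protocol is silent on group 4, and the stopping reason is the one item that existing records would not reveal. But silence in a summary form that asks for a brief account of procedures does not show that staff would withhold the questionnaire, or that the forms lack such a field; the forms are not in the document. The large figures need both a wide gap in completion between arms and almost complete dissatisfaction among those who stop, and the protocol supports neither. The 33-50% refusal in Background and Significance cannot stand in for a stopping rate: it describes patients who decline when approached for the current screening, a step that in this trial comes before randomisation.

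**Conclusion.** No change to the plan is called for. Satisfaction with a process has to be asked after the process, and the sentence does no more than place it there. It contains no rule that leaves out people who stopped early, and nothing the protocol states is shown to give a wrong result.

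The remaining gap is narrow: participants who quit the screener but neither withdraw nor are stopped by the clinical team. A research assistant would sensibly still offer them the questionnaire. Recording why someone stopped is a matter for the forms; completion by assigned arm and any sensitivity analysis are matters for an analysis plan.

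With 70% true satisfaction and 30-50% among non-completers, the false difference is about 1 to 2 points at 90% v. 95% completion and at most 7.9 points at 80% v. 95%, against about 16 points detectable upward. It is zero when loss and the satisfaction of non-completers are equal in the two arms. These figures rest wholly on assumed rates. The conclusion would weaken if stopping proved common, clearly different by mode and concentrated among dissatisfied patients; the count of missing questionnaires by arm would give the first warning of that.

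### Does inviting every Spanish speaker to interview contradict the four balanced groups and the anticipated 48 interviews?

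*Protocol*

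**What the plan says.** The interview plan is in the Protocol under Research Design and Methods.

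- **Groups:** "We will purposively sample to balance recruitment across 4 groups defined by screening strategy (oral v. iPad) and health literacy (high v. limited"). The aim given for this sampling is to bring out the full range of themes within each group.
- **Stopping:** "We will enroll in the interview portion of the study until thematic saturation is reached in each of the four groups".
- **Size:** the plan disclaims any formal size for the qualitative part. It cites the general experience that "thematic saturation is generally reached by 12 interviews per group" and draws its total from this: "therefore we anticipate completing 48 interviews".
- **Language:** the rule is that "all Spanish-speaking patients will be invited to participate in the qualitative interview to ensure a diverse representation of perspectives". The reason offered is that relatively few Spanish speakers are expected in this emergency department.

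The same section has every participant take the Newest Vital Sign and be randomized to oral or iPad screening, 100 per arm. It gives no expected number of Spanish speakers and no literacy distribution by language. It does not say whether their interviews count toward the four groups, or whether they are still invited once their group is saturated.

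**The concern.** The figure of 48 is built from four groups of 12, and language is not one of the two dimensions that define them. The next sentence then invites all Spanish speakers, without a cap and whatever their group. Three worries follow.

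1. The invitations might overfill some groups or add a block of interviews that the 48 does not include.
2. If Spanish speakers fall mainly in the limited-literacy groups, those groups become largely Spanish-speaking and the high-literacy groups largely English-speaking. A difference in themes by literacy could then be a difference by language.
3. Saturation is never judged among Spanish speakers, although their perspective is the reason for the rule.

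At stake would be the reading of limited-literacy views, in which the Consent Procedures section declares a particular interest, and the interview workload.

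**Working it through.** **The plan's own figure.** 4 groups × 12 interviews = 48, as stated.

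**Do the rules exclude each other?** Set side by side, one rule governs how many interviews each group needs (until saturation) and the other governs who is asked first (all Spanish speakers). Each Spanish speaker has a literacy result and a randomized modality, so an interview with that person is an interview in one of the four groups. Inviting them all and filling the remaining places from English speakers satisfies both sentences, provided Spanish speakers alone do not overfill a group.

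**When would they overfill a group?** Inputs from the protocol: 200 enrolled, 1:1 modality split, 12 interviews per group. Assumptions, since the protocol gives no figures: *s* = Spanish-speaking share, *a* = share accepting the interview, *l* = share of Spanish speakers with limited literacy.

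- Spanish speakers per limited-literacy group = 200·*s*·*a*·*l* / 2
- Spanish speakers per high-literacy group = 200·*s*·*a*·(1 − *l*) / 2
- Total = sum over the four groups of the larger of 12 and the Spanish-speaking count

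A limited-literacy group passes 12 when 100·*s*·*a*·*l* > 12, that is, *s*·*a*·*l* > 0.12. The totals below are evaluated at expected counts; chance variation can add a few where a count lies near or above 12.

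| *s* | *a* | *l* | Per limited group | Per high group | Total |
|---|---|---|---|---|---|
| 10% | 100% | 60% | 6 | 4 | 48 |
| 10% | 100% | 80% | 8 | 2 | 48 |
| 20% | 50% | 60% | 6 | 4 | 48 |
| 20% | 50% | 80% | 8 | 2 | 48 |
| 20% | 100% | 60% | 12 | 8 | 48 |
| 20% | 100% | 80% | 16 | 4 | 16 + 16 + 12 + 12 = 56 |

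At *s* = 10% and *a* = 50% the counts are lower still (3-4 per limited-literacy group) and the total is 48. At *s* = 10% with all accepting and *l* = 90%, the chance that a given limited-literacy group exceeds 12 is 5.8%.

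Much larger totals need one of two things. The first is to count no Spanish speaker toward any group: 48 + 20 = 68 to 48 + 40 = 88 if all accept, or 58 to 68 if half do. The second is an extreme share: *s* = 30%, all accepting and *l* = 90% gives 27 + 27 + 12 + 12 = 78. The protocol expects Spanish speakers to be relatively few.

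**Language mix within the groups.** With 20 Spanish speakers (*s* = 10%), all accepting:

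| *l* | Limited-literacy group | High-literacy group |
|---|---|---|
| 50% | 5/12 = 42% | 5/12 = 42% |
| 70% | 7/12 = 58% | 3/12 = 25% |
| 90% | 9/12 = 75% | 1/12 = 8% |

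An imbalance can therefore arise within 48 interviews, but only if language and literacy are associated.

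**The case for a change.** The strongest case for a change needs no assumed numbers. Suppose a Spanish speaker enrols after their group is saturated. The stopping rule says interviews in that group are finished; the language rule says to invite. Nothing says which prevails. With about 48 interviews expected from 200 participants, groups may well saturate before enrolment ends. The rule also oversamples by language on purpose: 20 Spanish speakers, all accepting, would be 20/48 = 42% of interviews. A separate Spanish-speaking group with its own saturation check would settle all of this for roughly 12 × $20 = $240 plus transcription.

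The silence on late invitations is real, but either reading leaves the results sound. An interview held after saturation does no harm to a search for the range of opinions. In the highest case on the 10-20% assumptions there are 56 − 48 = 8 extra interviews, or 8 × $20 = $160 plus transcription. Groups close on saturation, not at 12, so if Spanish speakers raise new themes their group stays open.

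The possible mixing of language and literacy also stands, as a possibility. If the two are associated, Spanish speakers would cluster in the limited-literacy groups without this rule too; the rule raises their number. An analyst coding the transcripts will know the interview language and can take it into account.

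The separate group is not a clear gain. Keeping Spanish speakers out of the four groups removes them from the limited-literacy groups, whose views the study especially wants. The fifth group would pool both modalities and both literacy levels. With 20 Spanish speakers and half accepting it would hold 10, short of the 12 the protocol treats as typical. The stated purpose is diversity of perspectives, which does not require saturation within a language subgroup.

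**Conclusion.** No change follows. The invite-all rule and the four-group plan can both be followed, and the 48 is an anticipated number that the rule does not contradict. With Spanish-speaking interviewees counted in the groups they belong to, a 10-20% share and 60-80% limited literacy give 48-56 interviews if all accept and 48 if half do. These shares are assumptions; at a 30% share with near-universal limited literacy the total would be well above 48, but it would still break no stated limit.

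The mixing of language with literacy rests on an association that the protocol does not state, and it affects a comparison of themes that the protocol does not set as an aim. The randomized comparison of oral with iPad screening is untouched. Whether invitations continue in a saturated group is an operational detail: the natural reading is that these interviews count toward the person's own group and may go beyond saturation.
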